### 8.3.2 DEFINITION OF SERIOUS ADVERSE EVENTS (SAE)

An adverse event (AE) or suspected adverse reaction is considered "serious" if, in the view of either the investigator or sponsor, it results in any of the following outcomes:

- death,
- a life-threatening adverse event,
- inpatient hospitalization or prolongation of existing hospitalization,
- a persistent or significant incapacity or substantial disruption of the ability to conduct normal life functions, or a congenital anomaly/birth defect.
- Important medical events that may not result in death, be life-threatening, or require hospitalization may be considered serious when, based upon appropriate medical judgment, they may jeopardize the participant and may require medical or surgical intervention to prevent one of the outcomes listed in this definition. Examples of such medical events include allergic

bronchospasm requiring intensive treatment in an emergency room or at home, blood dyscrasias or convulsions that do not result in inpatient hospitalization, or the development of drug dependency or drug abuse.

The following hospitalizations are not considered to be SAEs:

- Routine treatment or monitoring of the studied indication, not associated with any deterioration in condition
- Elective or pre-planned treatment for a pre-existing condition that is unrelated to the indication under study and has not worsened since signing the informed consent
- Social reasons and respite care in the absence of any deterioration in the participant's general condition
- Hospitalization due solely to progression of the underlying cancer
- Events that are clearly related to surgical complications experienced as a result of the craniotomy and not related to study participation or the test article(s) should not be recorded as AEs. If there is any indication that the event may be related to study participation or the test article, the event should be recorded as an adverse event.

For any of the above, any associated AEs or complications should be reported as an SAE if the AE prolongs hospitalization or otherwise meet the criteria for an SAE.

### 8.3.3 CLASSIFICATION OF AN ADVERSE EVENT

#### 8.3.3.1 SEVERITY OF EVENT

The severity of an AE should be defined according to the National Cancer Institute (NCI) Common Toxicity Criteria Adverse Events (CTCAE) Version 5.0. AEs that are not described in the NCI CTCAE should be evaluated using the following guidelines:

- 1 = Mild AE: Awareness of symptom, but easily tolerated; usually transient requiring no special treatment; does not interfere with usual status or activities
- 2 = Moderate AE: May be ameliorated by simple therapeutic measures; may interfere with usual activities
- 3 = Severe AE: Incapacitating, inability to perform usual activities
- 4 = Life threatening consequences; urgent intervention indicated
- 5 = Fatal AE

#### 8.3.3.2 RELATIONSHIP TO STUDY INTERVENTION

All adverse events (AEs) must have their relationship to study intervention assessed by the clinician who examines and evaluates the participant based on temporal relationship and his/her clinical judgment. The degree of certainty about causality will be graded using the categories below. In a clinical trial, the study product must always be suspect.

- **Definitely Related** – There is clear evidence to suggest a causal relationship, and other possible contributing factors can be ruled out. The clinical event, including an abnormal laboratory test result, occurs in a plausible time relationship to study intervention administration and cannot be explained by concurrent disease or other drugs or chemicals.
- **Probably Related** – There is evidence to suggest a causal relationship, and the influence of other factors is unlikely. The clinical event, including an abnormal laboratory test result, occurs within a

reasonable time after administration of the study intervention, is unlikely to be attributed to concurrent disease or other drugs or chemicals, and follows a clinically reasonable response on withdrawal.

- **Potentially Related** – There is some evidence to suggest a causal relationship (e.g., the event occurred within a reasonable time after administration of the trial medication). However, other factors may have contributed to the event (e.g., the participant's clinical condition, other concomitant events). Although an AE may rate only as "possibly related" soon after discovery, it can be flagged as requiring more information and later be upgraded to "probably related" or "definitely related", as appropriate.
- **Unlikely to be related** – A clinical event, including an abnormal laboratory test result, whose temporal relationship to study intervention administration makes a causal relationship improbable (e.g., the event did not occur within a reasonable time after administration of the study intervention) and in which other drugs or chemicals or underlying disease provides plausible explanations (e.g., the participant's clinical condition, other concomitant treatments).
- **Not Related** – The AE is completely independent of study intervention administration, and/or evidence exists that the event is definitely related to another etiology.

#### 8.3.3.3 EXPECTEDNESS

The Safety Officer will be responsible for determining whether an adverse event (AE) is expected or unexpected. An AE will be considered unexpected if the nature, severity, or frequency of the event is not consistent with the risk information previously described for the study intervention.

#### 8.3.4 TIME PERIOD AND FREQUENCY FOR EVENT ASSESSMENT AND FOLLOW-UP

The occurrence of an adverse event (AE) or serious adverse event (SAE) may come to the attention of study personnel during study visits and interviews of a study participant presenting for medical care, or upon review by a study monitor.

All AEs including local and systemic reactions will be captured on the appropriate case report form (CRF). Information to be collected includes event description, time of onset, clinician's assessment of severity, relationship to study product (assessed only by those with the training and authority to make a diagnosis), and time of resolution/stabilization of the event. All AEs occurring while on study must be documented appropriately regardless of relationship. All AEs will be followed to adequate resolution.

Any medical condition that is present at the time that the participant is screened will be considered as baseline and not reported as an AE. However, if the study participant's condition deteriorates at any time during the study, it will be recorded as an AE.

Changes in the severity of an AE will be documented to allow an assessment of the duration of the event at each level of severity to be performed. AEs characterized as intermittent require documentation of onset and duration of each episode.

The Investigator will record adverse events from the time of treatment until 7 days after the last day of study participation (for non-serious AEs). All serious adverse events will be recorded with start dates occurring any time after informed consent is obtained until 30 days (for SAEs) after the last day of study participation. At each study visit, the investigator will inquire about the occurrence of AE/SAEs since the last visit. Events will be followed for outcome information until resolution or stabilization.

### 8.3.5 ADVERSE EVENT REPORTING

The site investigator or designee will record adverse events. Investigator or designee should use correct medical terminology/concepts when recording AEs on the Adverse Event CRF. Avoid colloquialisms and abbreviations.

Only one AE term should be recorded in the event field on the Adverse Event CRF.

For all AEs, a diagnosis (if known) should be recorded on the Adverse Event eCRF rather than individual signs and symptoms. However, if a constellation of signs and/or symptoms cannot be medically characterized as a single diagnosis or syndrome at the time of reporting, each individual event should be recorded on the Adverse Event CRF. If a diagnosis is subsequently established, all previously reported AEs based on signs and symptoms should be nullified and replaced by one AE report based on the single diagnosis, with a starting date that corresponds to the starting date of the first symptom of the eventual diagnosis.

#### 8.3.5.1 PERSISTENT/RECURRENT AE

A persistent AE is one that extends continuously, without resolution, between participant evaluation time points. Such events should only be recorded once on the Adverse Event CRF. The initial severity of the event should be recorded, and the severity should be updated to reflect the most extreme severity any time the event worsens. If the event becomes serious, the Adverse Event CRF should be updated to reflect this.

A recurrent AE is one that resolves between participant evaluation time points and subsequently recurs. Each recurrence of an AE should be recorded separately on the Adverse Event CRF.

### 8.3.6 SERIOUS ADVERSE EVENT REPORTING

The site investigator or designee will report to IBTC-CC, any serious adverse event (SAE), whether or not considered study intervention related, including those listed in the protocol or investigator brochure and must include an assessment of whether there is a reasonable possibility that the study intervention caused the event. Study endpoints that are serious adverse events (e.g., all-cause mortality) must be reported in accordance with the protocol unless there is evidence suggesting a causal relationship between the study intervention and the event (e.g., death from anaphylaxis). In that case, the investigator must immediately report the event to the IBTC-CC. Cancer progression and cancer-related death are a study endpoint and will not be reported as an AE.

Information about all SAEs is collected and recorded on the Serious Adverse Event Report Form; all applicable sections of the form must be completed in order to provide a clinically thorough report. The investigator must assess and record the relationship of each SAE to each specific study treatment (if there is more than one study treatment), complete the SAE Report Form, and send the completed, signed form [[contact]](mailto:[contact]) within **24 hours** of determining the adverse event as serious.

The original copy of the SAE Report Form must be kept at the study site.

All SAEs will be followed until satisfactory resolution or until the site investigator deems the event to be chronic or the participant is stable. Other supporting documentation of the event may be requested by the IBTC-CC and should be provided as soon as possible.

IBTC-CC will be responsible for notifying the Food and Drug Administration (FDA) of any unexpected fatal or life-threatening suspected adverse reaction as soon as possible, but in no case later than 7 calendar days after IBTC-CC's initial receipt of the information. In addition, IBTC-CC must notify FDA and all

## A Phase 0 Study of Infigratinib in Recurrent Glioblastoma Patients Protocol 2020-08

participating investigators in an Investigational New Drug (IND) safety report of potential serious risks, from clinical trials or any other source, as soon as possible, but in no case later than 15 calendar days after the IBTC-CC determines that the information qualifies for reporting.

### 8.3.7 REPORTING EVENTS TO PARTICIPANTS

Adverse events affecting a study participant on an individual level will be reported to that participant by the primary investigator as soon as they are known. Events affecting other study participants will be reported by the principal investigator to study participant(s) if the information may impact the decision to participate in the trial. Modification of the informed consents will be implemented if there are newly recognized risks. Previously enrolled participants will be reconsented as per required by IRB and institutional guidelines.

### 8.3.8 EVENTS OF SPECIAL INTEREST

AESIs for infigratinib have not yet been defined in the Investigator's Brochure.

### 8.3.9 REPORTING OF PREGNANCY

Pregnancy is not considered an adverse event unless it is a spontaneous abortion. Each pregnancy occurring while the participant is on study treatment must be reported to IBTC-CC within 24 hours of learning of its occurrence. Participants who become pregnant during the trial must be withdrawn. The pregnancy will be followed up from the estimated date of delivery plus 3 months to determine outcome, including spontaneous or voluntary termination, details of the birth, and the presence or absence of any birth defects, congenital abnormalities, or maternal and/or newborn complications.

Women of childbearing potential should be advised to use highly effective contraception methods while they are receiving study treatment and up to 3 months after treatment has been stopped.

## 8.4 UNANTICIPATED PROBLEMS

### 8.4.1 DEFINITION OF UNANTICIPATED PROBLEMS (UP)

The Office for Human Research Protections (OHRP) considers unanticipated problems involving risks to participants or others to include, in general, any incident, experience, or outcome that meets all of the following criteria:

- Unexpected in terms of nature, severity, or frequency given (a) the research procedures that are described in the protocol-related documents, such as the Institutional Review Board (IRB)-approved research protocol and informed consent document; and (b) the characteristics of the participant population being studied;
- Related or possibly related to participation in the research ("possibly related" means there is a reasonable possibility that the incident, experience, or outcome may have been caused by the procedures involved in the research); and
- Suggests that the research places participants or others at a greater risk of harm (including physical, psychological, economic, or social harm) than was previously known or recognized.

### 8.4.2 UNANTICIPATED PROBLEM REPORTING

The investigator will report unanticipated problems (UPs) to the reviewing Institutional Review Board (IRB) and to the IBTC-CC. The UP report will include the following information:

A Phase 0 Study of Infigratinib in Recurrent Glioblastoma Patients  
Protocol 2020-08

- Protocol identifying information: protocol title and number, PI's name, and the IRB project number;
- A detailed description of the event, incident, experience, or outcome;
- An explanation of the basis for determining that the event, incident, experience, or outcome represents an UP;
- A description of any changes to the protocol or other corrective actions that have been taken or are proposed in response to the UP.

To satisfy the requirement for prompt reporting, UPs will be reported using the following timeline:

- UPs that are serious adverse events (SAEs) will be reported to the IRB and to the IBTC-CC within 7 days of the investigator becoming aware of the event.
- Any other UP will be reported to the IRB and to the IBTC-CC within 14 days of the investigator becoming aware of the problem.
- All UPs should be reported to appropriate institutional officials (as required by an institution's written reporting procedures), the supporting agency head (or designee), and the Office for Human Research Protections (OHRP) within approximately 1 month of the IRB's receipt of the report of the problem from the investigator.

---

#### 8.4.3 REPORTING UNANTICIPATED PROBLEMS TO PARTICIPANTS

Unanticipated problems affecting the study or study participants will be reported to participants by the primary investigator as soon as they are known. Modification of the informed consents will be implemented if there are newly recognized risks. Previously enrolled participants will be reconsented as per required by IRB and institutional guidelines.

## 9 STATISTICAL CONSIDERATIONS

### 9.1 STATISTICAL HYPOTHESES

The phase 0 study will be conducted as an open-label, multi-institution study (up to 3 sites) with 20 patients in the phase 0 component and progression-free-survival (PFS) determination in the expansion cohort. The clinical trial will be considered an exploratory study to study the PK and PD effect of infigratinib from intra-operative tumor tissue and no formal statistical comparison or hypotheses will be carried out. Thus, the outcome will be summarized with descriptive statistics (N, median, mean, standard deviation, minimum, maximum and the 80% of confidence interval [CI] for the mean). The 80% confidence level is appropriate for a phase 0 study with small sample size.

If, after the study has begun, changes are made to primary and/or key secondary hypotheses, or the statistical methods related to those hypotheses, then the protocol will be amended. Changes to exploratory or other non-confirmatory analyses made after the protocol has been finalized, along with an explanation as to when and why they occurred, will be listed in results for the study. Post hoc exploratory analyses will be clearly identified. No separate Statistical Analysis Plan (SAP) will be issued for this study.

### 9.2 SAMPLE SIZE DETERMINATION

Historically, the Ivy Center operates on 400 recurrent high-grade glioma patients per year. If 5% of the patients carrying FGFR3 fusion or FGFR1/3 mutations, we expect 20 patients to be eligible for study each year. Assuming 50% patient capture, we envision 10 patients per year to be enrolled in the trial. The duration of the trial is therefore designed to be 24 months with an additional 6 months for clinical follow-up of participants enrolled into expansion cohort (estimated at 50% of the Phase 0 cohort).

### 9.3 POPULATIONS FOR ANALYSES

- Safety Analysis Dataset: participants who took at least one dose of study intervention
- PK Analysis Dataset: All participants who undergo surgery and are assessed for the PK endpoint in Phase 0
- Efficacy Analysis Dataset: The subset of participants who meet the PK criteria in Phase 0 and begin at least one day of treatment on Expansion Cohort.
- PD Analysis Dataset: All participants with evaluable PD data assessable for the PD secondary endpoints

### 9.4 STATISTICAL ANALYSES

#### 9.4.1 ANALYSIS OF THE PRIMARY EFFICACY ENDPOINT(S)

Phase 0 endpoint PK Analysis:

A positive PK response will be unbound concentrations of infigratinib (along with its active metabolites) reaching 5-fold higher than their respective cell-free biochemical IC50 values within the non-enhancing region of the tumor.

Expansion cohort endpoint: For the primary endpoint of PFS rate at 6 months:

- Progression-free survival (PFS) is defined as the number of days from the date of surgery to the first documentation of progression or death due to any cause. Participants who remain alive without progression will be censored for PFS at the date of their last tumor assessment.

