Pharmacokinetic (PK) blood sample		Pre			X 		1, 8, 15	1, 8, 15				
Pharmacokinetic (PK) CSF sample					X 							
Pharmacokinetic (PK) tumor sample					X 							
Pharmacodynamic (PD) blood sample		Pre										
Pharmacodynamic (PD) tumor sample	Archival/ biopsy				X 							
Pharmacogenomic (PG) tumor tissue	Archival/ biopsy											
Patient Derived Xenograft (PDX) tumor sample					X 							
IMAGING PROCEDURES												
MRI – Brain with/without contrast	X 					X 	MRI Q3 months 		Last			
RANO						X	Q3 months		Last			
ADMINISTRATIVE PROCEDURES												
Complete Case Report Forms (CRFs)	X	X		X	X	X	X	X	X	X	X	X
1. Expansion Cohort: study drug administration is every day (QD) 3 weeks on/ 1 week off 2. Screening assessment may be completed at D1 pre-dose, if completed at screening, does not need to be repeated at D1 pre-dose except for ECG and ECOG. Results must be available to confirm eligibility prior to dosing.												

A Phase 0 Study of Infigratinib in Recurrent Glioblastoma Patients

Protocol 2020-08

Procedures	Phase 0						Expansion				Safety Phone Call ~30 days after last dose	Survival Follow Up Phone Call / Letter
	Screening Day -28 to -1	Enrollment/Baseline Day 1	Days 2-5	Pre-surgical Assess. Day 6	Surgical Visit Day 7	Post-op Follow Up ~7 days after last dose	Cycle 1 (28 days) 	Cycle 2 (28 days) 	Subsequent Cycles (28 days) 	End of Study Treatment		

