
3. Single ECG. At Screening: If the QTcF is >470 msec in the first ECG, a total of 3 ECGs separated by at least 5 minutes should be performed. If the average of these 3 consecutive results for QTcF is ≤470 msec, the participant meets eligibility in this regard.
 
4. See Section 8.2.12.
 
5. Serum pregnancy test (women of childbearing potential) at screening. Urine pregnancy test (women of childbearing potential) at remaining visits pre-dose (if applicable).
 
6. PK blood samples will be obtained on D1 pre-dose and on D7 at pre-dose (trough level), 0.5, 1, 2, 4, 6, 8, 24 (trough) hours post dose (<math>\pm</math>5 min window for 0.5hr and 1hr; <math>\pm</math>15min window for 2, 4, 6hr; <math>\pm</math>1hr for 8 and 24 hours post dose).
 
7. PK CSF, Tumor and blood samples will be collected intra-operatively at approximately 8 hours post-dose (<math>\pm</math>1 hour)
 
8. PD/PDX Tumor sample will be collected intra-operatively at approximately 8 hours post-dose (<math>\pm</math>1 hour)
 
9. MRI completed as Routine Care. At screening, utilize the most recent MRI available. At follow-up, utilize the first MRI obtained post-operatively.
 
10. The start of follow up for long-term survival begins following completion of the Day 30 safety follow up call.
 
11. Ophthalmic exam should include visual acuity testing (including corrected distance acuity), slit lamp examination of the anterior eye segment, intraocular pressure (IOP), retinal OCT and dilated fundoscopy. Additional examinations such as specular microscopy and corneal pachymetry will be performed as clinically indicated. In addition, ophthalmic exams should be done as clinically indicated.
 
12. A visit window of <math>\pm</math>1 day in Cycle 1 and 2 on Days 1, 8, and 15 and <math>\pm</math>3 days in Cycle 3 onward is allowed.
												

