### 3 OBJECTIVES AND ENDPOINTS

Objectives & Endpoints:	Objectives	Endpoints
Primary	1. Phase 0: To measure the pharmacokinetic (PK) effects of infigratinib in recurrent high-grade glioma participants.	1. Phase 0: Total and Unbound infigratinib concentration in enhancing and non-enhancing tumor tissue (8hr), plasma (0-24H) and CSF (8hr) will be determined.
	2. Expansion Cohort: Examine progression-free survival in recurrent high-grade glioma participants with demonstrated PK effects	2. Expansion Cohort: 6-month Progression-free survival (PFS6) rate from time of surgery to date of recurrence
Secondary	1. Phase 0: PD Analysis	1. Phase 0: percentage of pERK+, MIB-1+ and Cleaved Caspase 3+ cells from the surgical tissue will be quantified and compared to baseline archival/biopsy tissue.
	2. Expansion cohort: To monitor safety and tolerability of study drug combinations in participants with recurrent high-grade glioma.	2. Expansion Cohort: Safety and tolerability: 
 
a. Drug-related toxicity
 
b. Number of Adverse Events through study completion, assessed up to 60 months
 
c. Treatment-emergent adverse events (TEAEs)
 
d. Deaths
 
e. Clinical laboratory abnormalities per CTCAE (Version 5.0)
 

Exploratory	1. Phase 0: Describe systemic PK	1. Phase 0: Systemic plasma PK profile parameters ( $T_{max}$ , $C_{max}$ , $t_{1/2}$ , $AUC_{0-24h}$ ) for total and unbound levels will be determined for infigratinib.
	2. Expansion cohort: Examine Overall Survival (OS) in recurrent high-grade glioma participants with demonstrated PK effects	2. Median Overall Survival (OS) from time of surgery to date of death from any cause

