#### 4.1.2 EXPANSION COHORT DESIGN

Participants with tumors demonstrating PK-response in Phase 0 will continue treatment with the same dose continuously for 21 days in 28d cycles after surgery. This will constitute the Expansion Cohort component of the study. PD biomarkers will be included for exploratory analyses. Expansion Cohort participants will be contacted every 3 months by letter or phone for collection of survival data.

Participants will be treated until unacceptable toxicity is observed, or until disease progression as assessed by RANO criteria.

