Asymptomatic amylase and/or lipase elevation Grade 3 ( $> 2.0 - 5.0 \times \text{ULN}$ )	
 
• Hold dose of infigratinib until resolved to CTCAE Grade <math>\leq 2</math>.
 
• <math>\downarrow 1</math> dose level of infigratinib
 
 
Note: A CT scan or other imaging study to assess the pancreas, liver, and gallbladder must be performed within 1 week of the first occurrence of any CTCAE <math>\geq</math> Grade 3 amylase and/or lipase.
 
If asymptomatic CTCAE Grade 2 elevations of lipase and/or amylase occur again at the reduced dose, patients will be discontinued permanently from study treatment.

Grade 4 ( $> 5.0 \times \text{ULN}$ )	Discontinue patient from study treatment
Hyperphosphatemia Serum phosphorus $> 5.5 - 7.0 \text{ mg/dL}$	See Table 4 Maintain dose level of infigratinib, but modify phosphate lowering therapy

A Phase 0 Study of Infigratinib in Recurrent Glioblastoma Patients

Protocol 2020-08

Worst Toxicity CTCAE v5.0 Grade (unless otherwise specified)	Recommended Dose Modifications any time during a cycle of therapy
Serum phosphorus >7.0 – 10.0 mg/dL despite phosphate lowering therapy	
Hold infigratinib dose until resolved to serum phosphorus <math>\leq</math> 5.5 mg/dL
 
 
if resolved by <math>\leq</math> 14 days after suspending infigratinib, <math>\downarrow</math> 1 dose level
 
if does not resolve within 14 days of suspending infigratinib, discontinue patient from the study.
 

Serum Pi $>$ 10.0 mg/dL	Discontinue patient from study treatment
Hypercalcemia Serum calcium grade 2	Hold infigratinib dose until resolved to grade 1 or baseline: 
 
if resolved <math>\leq</math> 7 days after suspending infigratinib, maintain dose level
 
if resolved <math>></math> 7 days after suspending infigratinib, <math>\downarrow</math> 1 dose level
 

Serum calcium $\geq$ grade 3	Discontinue patient from the study
Nervous system disorders	
Neurotoxicity Grade 2	Omit dose of infigratinib until resolved to CTCAE Grade $\leq$ 1, then $\downarrow$ 1 dose level of infigratinib
Grade $\geq$ 3	Discontinue patient from study drug treatment
GI disorders	
Pancreatitis Grade $\geq$ 2	Discontinue patient from study drug treatment

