## 7 STUDY INTERVENTION DISCONTINUATION AND PARTICIPANT DISCONTINUATION / WITHDRAWAL

### 7.1 DISCONTINUATION OF STUDY INTERVENTION

Discontinuation from treatment does not mean discontinuation from the study, and remaining study procedures should be completed as indicated by the study protocol. If a clinically significant finding is identified (including, but not limited to changes from baseline) after enrollment, the investigator or qualified designee will determine if any change in participant management is needed. Any new clinically relevant finding will be reported as an adverse event (AE).

The data to be collected at the time of study intervention discontinuation will include the end-of-study (EOS) procedures as shown in Section 1.2.

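### An Expansion participant who stops infigratinib alive and progression-free before month 6 has no later tumor assessment listed, so primary PFS6 status is not observed

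*Combined protocol and SAP*

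**What the plan says.** - **Endpoint.** Section 3 gives the primary Expansion endpoint as "6-month Progression-free survival (PFS6) rate from time of surgery to date of recurrence". Section 9.4.1 defines PFS as "the number of days from the date of surgery to the first documentation of progression or death due to any cause", so death is an event. It also counts removal from treatment for symptomatic deterioration as progression.
- **Censoring.** Section 9.4.1: "Participants who remain alive without progression will be censored for PFS at the date of their last tumor assessment". Section 9.4.5 rules out imputing missing efficacy data.
- **Imaging.** The Schedule of Activities (Section 1.2) has a post-operative MRI, then "MRI Q3 months 9" in the Expansion columns (the 9 is a footnote mark), then a last assessment. The RANO row follows the same pattern. Neither row has an entry under the 30-day safety call or survival follow-up. Footnote 9 adds "MRI completed as Routine Care".
- **Contact.** The synopsis has Expansion participants attending clinic until treatment ends. Section 4.1.2: "Expansion Cohort participants will be contacted every 3 months by letter or phone for collection of survival data".
- **Stopping.** Section 6.1.2 foresees stops for toxicity and for other reasons. Section 7.1 says "Discontinuation from treatment does not mean discontinuation from the study" and asks that the remaining procedures be completed as the protocol indicates. Some Table 3 entries read differently; the row for hyperphosphatemia that does not resolve says "discontinue patient from the study".
- **Analysis sets.** The Efficacy Analysis Dataset (Section 9.3) takes PK-positive participants with at least one day of Expansion treatment. Section 8.1.4 calls evaluable only those with at least one cycle and an Expansion MRI.
- **Estimator.** Section 9.4.1 names none for the PFS6 rate. Section 9.4.6 names Kaplan-Meier, for OS only.

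**The concern.** PFS6 needs each participant's progression status about six months after surgery, whether or not the drug is still being taken. The schedule ties tumor assessment to treatment. Table 3 contains many stops that have nothing to do with progression: creatinine, bilirubin, transaminases, pancreatitis, ocular events, neurotoxicity, and a dose delay of more than 14 days. Someone who stops early for one of these stays in the Efficacy Analysis Dataset, but nothing later is listed that would show whether the tumor has progressed.

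What remains is uneven. A death after stopping is found through survival contact and counted. A survivor is censored at the last scan, progressed or not. Section 2.1.1 says these tumors always recur, so unrecorded progression is a realistic possibility. In a cohort of about 10, one such person visibly moves the only primary efficacy figure, and a progression date that was not collected may not be recoverable later.

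**Working it through.** **1. Cohort size (Section 9.2).** 400 operations a year × 5% = 20 eligible; × 50% capture = 10 enrolled a year; × 2 years = 20, which agrees with the planned 20; × 50% entering Expansion = 10. The plan's figures reproduce.

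**2. Where month 6 falls.** With the conversion in Section 9.4.5, 6 × 30.4375 = 182.6 days after surgery. Assume Cycle 1 starts 7 to 28 days after surgery (the documents give no figure). The cycle running at month 6 is then (182.6 − 7)/28 + 1 = 7.3 down to (182.6 − 28)/28 + 1 = 6.5, so Cycle 7 or Cycle 6. A stop without progression in roughly Cycles 1 to 6 is exposed.

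**3. What the plan does with a participant who stops treatment.**

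| Course | Treatment under Section 9.4.1 | PFS6 status |
|---|---|---|
| Dies before month 6 | Event | Known |
| Removed for symptomatic deterioration before month 6 | Counted as progression | Known |
| Stops later, last scan at or after about day 183, no progression | Censored after month 6 | Known |
| Stops earlier without progression, alive at month 6 | Censored at last scan; no later assessment listed | Not observed |

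Only the last row is the problem.

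**4. Size.** Let n = 10, x = number known to be progression-free at month 6, m = number unobserved. The true proportion lies between x/n and (x + m)/n, a width of m/n. With x = 3 (assumed):

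| m (assumed) | Range | Width | Observed cases only |
|---|---|---|---|
| 1 | 3/10 to 4/10 = 30–40% | 10 points | 3/9 = 33% |
| 2 | 3/10 to 5/10 = 30–50% | 20 points | 3/8 = 38% |
| 3 | 3/10 to 6/10 = 30–60% | 30 points | 3/7 = 43% |

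The width depends only on m. With x = 4 and m = 2 the range is 40–60%, again 20 points.

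**5. Kaplan-Meier illustration (all times assumed).** Three events at day 90, two at day 180, three participants followed past month 6, and two who stop and are censored at day 60.
- As the plan would record it: (1 − 3/8) × (1 − 2/5) = 0.625 × 0.6 = 37.5%.
- If both had progressed at day 90: (1 − 5/10) × (1 − 2/5) = 30%.
- If both were progression-free at month 6: (1 − 3/10) × (1 − 2/7) = 50%.

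The estimate lies inside the range and can be off in either direction.

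**The case against.** The strongest reply is that the plan is unclear rather than closed on this.

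- The end of imaging is inferred from the schedule; no sentence states it. The merged cells leave some doubt about which column the last MRI entry belongs to, although the visit row uses the same label for End of Study Treatment.
- Section 9.4.1 censors at the last tumor assessment, not the last one on treatment, and MRI is routine care, so a later scan could count.
- Section 9.2 reserves six more months for clinical follow-up of the Expansion Cohort, Section 7.1 keeps people on study, and Section 8.2.11 asks for samples at a repeat craniotomy for recurrence.

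This stands as far as it goes: some later scans or recurrences may come to light. But nothing requires them to be obtained, read by RANO or recorded. Section 7.1 continues only procedures the protocol lists, and on either reading of the MRI row none is listed after the last assessment.

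A second reply is that the trial is exploratory. Section 9.1 plans no hypothesis test, and no PFS6 threshold or comparator is set. Ten participants also give little precision: 3 of 10 has an exact 80% interval of 12% to 55%. This lowers the priority. It does not remove the point, because a descriptive rate still needs observed outcomes.

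A reader might infer three stronger things that the documents do not support:
- That everyone who stops without progression is censored before month 6. Deaths, symptomatic deterioration and later stops are covered (step 3).
- That PFS6 is biased upward. People who stop for toxicity may do worse, but no text establishes this.
- That PFS6 would describe only those who tolerate the drug. Section 9.3 keeps early stoppers in the analysis set, and no estimator that drops them is named.

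For stops during Cycle 1 it is not even settled whether the participant is censored or non-evaluable, because Sections 8.1.4 and 9.3 differ.

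**Conclusion.** The gap is real and limited. It affects Expansion participants who stop before about day 183 after surgery without progression, stay alive, and were not removed for symptomatic deterioration. Followed as written, the plan leaves their PFS6 status unobserved. Counting later deaths while censoring survivors at the last scan makes that censoring potentially informative, in a direction that cannot be determined from the documents.

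Each case is worth 1/10 = 10 percentage points if about 10 participants enter the Expansion Cohort. The number of cases is an assumption throughout, since no discontinuation rate is given. This should be fixed as a cheap improvement; it does not undermine the Phase 0 part or the descriptive purpose of the trial.

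**What to change.** - **Schedule of Activities and Section 9.4.1.** State that, for Expansion participants who stop treatment without progression, routine-care MRI/RANO, clinical progression status and the start of any new antitumor therapy are collected at the existing 3-month interval until progression, death or the month-6 assessment. Add progression status to the existing 3-monthly contact.
- **Estimator.** Name the estimator for the PFS6 rate, so that it is clear how a censored participant enters it.
- **Study discontinuation.** Reconcile Section 7.1 with the Table 3 entries that take patients off the study itself (recurrent QTcF prolongation or ventricular arrhythmia, unresolved hyperphosphatemia, hypercalcemia, vomiting). The question is only whether outcome follow-up continues; no treatment-stopping rule needs to change.
- **Evaluability.** Reconcile Section 8.1.4 with the Efficacy Analysis Dataset in Section 9.3.

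The cost is protocol wording, a few extra CRF entries and some records to be obtained from outside providers. No study-only scan is added. It is best done before Expansion data accrue.
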